## 5.2 ASSESSMENT OF SAFETY

- **Positive and Negative Syndrome Scale (PANSS)** will be used to evaluate broad psychopathology associated with schizophrenia disease state.

The PANSS has 30 items. Each is rated from 1 to 7 points. The total factor score is the summation of the actual points for each item, leading the total score ranging from 30 to 210. [[R13-5061](#)].

It contains seven positive symptom items, seven negative symptom items and 16 general psychopathology symptom items. Fourteen of the PANSS items require input from a study partner. A trained rater interviews the patient and the study partner, estimated to take 30-40 minutes for evaluating the subjects' disease state.

- **Extrapyramidal Symptoms (EPS) will be assessed using 3 scales:**
  - The Simpson Angus Scale (SAS) is a performance scale that measures drug-induced parkinsonism symptoms. The rater asks the patient to perform 10 tasks and rates responses on a scale of 0-4 (normal to severe). It consists of one item measuring gait (hypokinesia), six items measuring rigidity and three items measuring glabella tap, tremor and salivation, respectively. A total score of 0-40 is calculated (or scale score can be calculated by dividing the total by 10 to give a score between 0 and 4).
  - The Abnormal involuntary movement scale (AIMS) records the occurrence of tardive dyskinesia (TD) in patients receiving antipsychotic medications. The AIMS test is used to

Proprietary confidential information © 2024 Boehringer Ingelheim International GmbH or one or more of its affiliated companies

detect TD and to follow the severity of a patient's TD over time. These items are also scored from 0 (= normal/healthy) to 4 (= severely affected). The scores are summed to give an overall score of the involuntary movements. It assesses tardive movement disorders.

- The Barnes Akathisia Rating Scale (BARS) is a rating scale that is administered by the investigator to assess the severity of drug-induced akathisia. The BARS is the most widely used rating scale for akathisia. The BARS is scored as follows: Objective Akathisia, Subjective Awareness of Restlessness and Subjective Distress Related to Restlessness are rated on a 4-point scale from 0 – 3 and are summed yielding a total score ranging from 0 to 9. In addition, Global Clinical Assessment of Akathisia is rated from 0-5.

- **Columbia Suicidality Severity Rating Scale (C-SSRS)**

The C-SSRS is a semi-structured, investigator-rated interview, developed by clinical experts in cooperation with the FDA, assessing both suicidal behavior and suicidal ideation. It does not give a global score but provides some categorical and some severity information specifically for behavior and ideation.

The computer-automated C-SSRS interview may be administered using a tablet device.

Subjects who do not have suicidal behavior or ideation will answer a limited number of questions and will usually complete the assessment in about 3 minutes. Subjects with significant suicidal ideation or behavior may require up to 10 minutes to answer all relevant questions. This assessment should be conducted early in the visit. At the conclusion of each assessment, the site will have access to the C-SSRS results. The results include the findings for suicidal ideation, intensity of ideation, suicidal behavior, and lethality / medical damage (for actual suicide attempts only).

The C-SSRS has been widely used in large multinational clinical trials. The C-SSRS will be administered first at screening (Visit 1) (using the 'Baseline / Screening' version) with the aim to exclude subjects with active moderate or severe symptomatology within a specified time prior to screening. The lifetime history of suicidal ideation and behavior will also be recorded.

After screening (Visit 1) the assessment 'since last visit' will be performed at each clinic visit ('Since Last Visit version'). The investigator is to review/ consider the C-SSRS results for plausibility and clinical relevance. Doubtful results may be repeated or results may be validated by a consulting psychiatrist. If there is a confirmed positive report of suicidal behavior or suicidal ideation type 4 or 5 after start of trial, the investigator is to immediately interview the subject during the clinic visit (if the investigator did not administer the C-SSRS leading to the positive report), and/ or is to consult a psychiatrist if considered necessary.

For any positive suicidal ideation (type 1 to 5) or suicidal behavior, the rater must document additional details in the comment fields in the C-SSRS in Pathway.

If there is any new suicidality or increase in suicidality, please comment on the clinical significance and any additional follow-up actions that may be performed in the eCRF.

If the positive report is confirmed, appropriate actions for the subject's safety have to be initiated and followed up as deemed necessary. The C-SSRS may be repeated at an unscheduled visit at the investigator's discretion.

C-SSRS results will be reported in terms of AEs as described in [Section 5.2.6.1.4](#).

### **5.2.1 Physical examination**

A complete physical examination will be performed at the time points specified in the [Flow Chart](#). It includes at a minimum general appearance, neck, lungs, cardiovascular system, abdomen, extremities, and skin.

Measurement of height and body weight will be performed at the time points specified in the Flow chart.

The results must be included in the source documents available at the site.

### **5.2.2 Vital signs**

Vital signs will be evaluated at the time points specified in the Flow Chart, prior to blood sampling.

This includes systolic and diastolic blood pressure and pulse rate (electronically or by palpation count for 1 minute) in a seated position after 5 minutes of rest. The results must be included in the source documents available at the site.

### **5.2.3 Safety laboratory parameters**

Safety laboratory parameters to be assessed are listed in [Table 5.2.3: 1](#). For the sampling time points please see the Flow Chart.

Patients do not have to be fasted for the blood sampling for the safety laboratory. All analyses will be performed by a central laboratory, the respective reference ranges will be provided in the lab manual in the ISF.

Instructions regarding sample collection, sample handling/ processing and sample shipping are provided in the Laboratory Manual in the ISF.

The central laboratory will send reports to the investigator (except for blinded Hb related parameters, for further details refer to [Section 4.1.5.1](#) and [Section 5.2.6.4](#)). Laboratory values that are out of range should be commented on lab report printouts and evaluated by the investigator for clinical significance.

Clinically significant abnormal laboratory results should be reported by the investigators in the eCRF either on baseline condition (from Visit 1 test) or on AE page (from subsequent visits test). Please refer to [Section 5.2.6](#).

Clinically relevant abnormal laboratory test results will need to be followed per investigators judgment, until normalization or stabilization or until an alternative explanation has been found.

Safety lab may be repeated for any or all lab parameters specified in the protocol, at any time point during the study, per investigators discretion.

In case the criteria for hepatic injury are fulfilled, a number of additional measures will be performed (please see [Section 5.2.6.1](#) and the DILI Checklist provided in the eDC system.) The amount of blood taken from the patient concerned will be increased due to this additional sampling.

The central laboratory will transfer the results of the analysis to the sponsor.

The site should not use a local laboratory to assess the Haematology parameters unless clinically justified.

Table 5.2.3:1

Safety laboratory tests

| Category  | Test name  |  |
|---|--|--|
| Haematology Panel A
(Refer Section 5.2.6.4 )  | Haemoglobin (Hb)
Haematocrit (Hct)
MCV, MCH, MCHC
RDW   | Red Blood Cell Count/ Erythrocytes
Reticulocyte Count
Reticulocyte index   |
| Haematology Panel B  | White Blood Cells/ Leukocytes

Diff. Automatic (manual if diff. automatic is abnormal)
- Neutrophils
- Eosinophils
- Basophils
- Monocytes
- Lymphocytes  | Platelet Count/ Thrombocytes

Total iron binding capacity (TIBC)
Serum ferritin
Serum iron

Folate
Vitamin B12  |
| Chemistry  | AST(GOT)
ALT(GPT)
Alkaline Phosphatase (AP)
Bilirubin Total, fractionated if increased
Creatine Kinase (CK)
CK-MB – only if CK is elevated
C-Reactive Protein
Gamma-Glutamyl Transferase (GGT/γ-GT)
Lipase
Amylase
Cholesterol, total
Triglycerides
Lactic Dehydrogenase (LDH) | Calcium
Sodium
Potassium
Glucose
HbA1c
Urea (BUN)
Creatinine
Estimated Glomerular filtration rate (eGFR) – using the CKD-EPI equation****
Protein, Total

TSH*
Prolactin* |
| Pregnancy test (females only)                                    | Human urine chorionic gonadotropin**
Serum Beta hCG, Qualitative (Only if human urine chorionic gonadotropin is positive)   |  |
| Urinalysis (quantitative)  | Urine creatinine   |  |
| Urinalysis (Qualitative)   | Urine Nitrite
Urine Protein
Urine Glucose
Urine Ketone
Urobilinogen  | Urine Bilirubin
Urine blood
Urine pH
Leukocyte esterase   |
| Urine Drug Screen ***
(Preliminary and confirmatory testing) | Amphetamines
Barbiturates
Cannabis
Cocaine  | Methadone
Opiates
PCP (Phencyclidine)  |

\*The following lab parameters will not be determined at each study visit:

- TSH – only at Visit 1
- Prolactin – only at Visit 2 and EOT/ eEoT

\*\* To be done at the site with the kit provided by the central lab.

\*\*\* Patients will be considered drug screen positive, if the confirmatory test is positive. Re-test is permitted at

visit 1a (refer to [Section 3.3](#)).

\*\*\*\*The eGFR will be derived from the serum creatinine value, age, sex and race using the Chronic Kidney Disease Epidemiology Collaboration (CKD-EPI) equation [[R12-1392](#)]. The race must be collected because the CKD-EPI equation uses race as an adjustment factor and therefore it is required for accurate estimation.

#### **5.2.4      Electrocardiogram**

The 12-lead ECGs will be performed as scheduled in the [Flow Chart](#). Twelve-lead ECGs (I, II, III, aVR, aVL, aVF, V1 – V6) will be recorded using equipment provided by a central ECG vendor. The ECGs will be recorded for at least 10-second duration after the subjects have rested for at least 5 minutes in a supine position and prior to lab sampling. Electrode placement will be performed according to the method of Einthoven/Goldberger (ankles and wrists). At all time points indicated in the Flow Chart, single ECGs will be recorded. ECG recordings at planned time points may be repeated for quality reasons like alternating current artefacts, muscle movements and electrode dislocation. In this case the repeated ECG recordings will be used if quality was better.

The investigator or a designee will evaluate whether the ECG is normal or abnormal and whether it is clinically significant, if abnormal. The electronic version of the ECG is regarded as source data. Dated and signed printouts will be stored in the patient's medical file if there is no validated and certified e-medical record for ECG data.

Additional ECGs may be collected by the investigator for safety reasons. Clinically relevant findings noticed at Visit 1 should be reported as baseline condition.

Clinically relevant abnormal findings noticed after Visit 1 will be reported as AEs and followed up and/or treated locally until normal or stable condition.

All ECGs will be transmitted electronically to the central ECG vendor for centralized and independent evaluation tThe vendor will provide a report to the site. Abnormalities detected during this centralized ECG evaluation will not necessarily qualify as an AE. Decisions on eligibility for the trial are the responsibility of the investigator. Abnormalities detected in central evaluation must be reviewed by the investigator and if considered clinically significant reported as baseline condition if identified at Visit 1 or as adverse event if identified at or after Visit 2. All clinically relevant abnormal findings will be managed as medically appropriate, per investigators clinical judgment

### 5.2.5 Other safety parameters

Assessment of disease state:

PANSS will be used to evaluate the disease severity. Refer to [Section 5.2](#). In addition investigator may use CGI-S and his/her clinical judgment for assessing schizophrenia worsening/relapse.

**Schizophrenia worsening (i.e., deterioration of chronic residual symptoms):** Fluctuation in the severity of symptoms is common and should be managed and reported as per the clinical judgment of the investigator. Adjustment of background medication is allowed when necessary. In such cases, schizophrenia worsening must be reported as adverse event per the clinical judgment of the investigator.

**Schizophrenia Relapse (acute episode):** If **severity** of schizophrenia symptoms fulfills the criteria of relapse (acute episode), investigator must report relapse as adverse event. Definition of relapse for this program is: Increased level of care (such as hospitalization, home hospitalization, emergency room (ER) visit due to psychotic symptoms) due to worsening of psychotic symptoms / increased PANSS per investigators judgment.

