#### **2.2.2.2      Further safety endpoints**

- Disease under study monitored using:
- PANSS total score and change from baseline
- Incidence of relapse
- SAS/BARS/AIMS Scale scores throughout the treatment
- Suicidality as assessed by C-SSRS
- Occurrence of protocol specified AESI
- Percentage of patients with (S)AEs (including clinically relevant abnormalities of physical examination, vital signs, ECG test and laboratory tests)

[REDACTED]

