| Executive Function | Planning ahead for an event, When someone changed plans, Coming up with solutions to problems, Figuring out new ways to do things   | 14, 15, 16, 17         | 4   |
| Attention          | My mind drifted off, Got distracted by things going on, Hard to focus on something, Thinking about things repetitively, Thoughts were racing, Thinking was unclear, cloudy, foggy                                     | 18, 19, 20, 21, 22, 23 | 3   |
| Sharp thinking     | Thinking was not as fast as others, When tired, thinking slowed, Thoughts were blocked  | 24, 25, 26             | 3   |
| NA                 | Overall bother in the past week   | 27                     |   |
| NA                 | Overall bother if thought stay the same   | 28                     |   |

- **Clinical Global impressions – Severity (CGI-S)** is a one-item evaluation completed by the clinician on the patient's severity of cognitive impairment. The CGI-S is rated ordinal from 1 to 4 (none, mild, moderate, severe). Ideally, the same investigator or site staff should assess CGI-S at all visits (refer also to [section 6.2.1](#) for additional requirements).
- **Clinical Global impressions – Change (CGI-C)** is a 5-point scale (much better, a little better, no change, a little worse, much worse) used to assess the change of the patient's status from start of the treatment and is completed by the clinician.
- **Study Partner Global Impression of Severity (SPGI-S)** is similar to CGI-S but completed by the study partner.
- **Study Partner Global Impressions of Change (SPGI-C)** a similar question as the CGI – C but completed by the study partner.
- **Patient Global Impressions-Severity (PGI-S)** is a 4-point scale with similar response categories as CGI-S, which requires the participant to rate the severity of their own symptoms.
- **Patient Global Impressions-Change (PGI-C)** measures a patient's belief about the efficacy of treatment. PGI-C is a 5-point scale with similar response categories as CGI-C, depicting a

Proprietary confidential information © 2024 Boehringer Ingelheim International GmbH or one or more of its affiliated companies

patient's rating of overall improvement since started taking the study medication and is completed by the patient.

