### 6.2 DETAILS OF TRIAL PROCEDURES AT SELECTED VISITS

#### 6.2.1 General requirements

The following requirements for the conduct of the assessments need to be followed:

- **The MCCB should be done as the first efficacy assessment preferably in the morning (depending on the sleep cycle of the patient), followed by VRFCAT, ToL and SCoRS.**
- All other assessments can be completed per the convenience of patient and site at all respective visits.
- It is very important to have the MCCB done at approximately the same time of day for each individual patient throughout the trial. The MCCB assessments at Visit 6 and (e)EoT Visit must be started at approximately the same time of the day as MCCB assessment at Visit 2 (+/- 60 minutes). In case this cannot be adhered to, then the visit should be rescheduled within the allowed visit window.
- Assessment of each rating scale should preferentially be done by the same rater for a given patient throughout the study period. However, for MCCB and VRFCAT, the consistency of time of day is more important than the consistency of the rater.
- The global impression anchor scales (CGI-S/CGI-C and/or PGI-S/PGI-C and/or SPGI-S/SPGI-C) should be assessed after SCoRS at the respective visits when they are scheduled. Similarly, patients should complete PGI-S/PGI-C after PRECIS is completed at the respective visits when these measurements are scheduled. If qualified, the SCoRS rater should preferably perform the CGI-S/CGI-C.
- The CGI rater should base their assessment after review of information about that patient at that visit for CGI-S or since start of treatment for CGI-C including the SCoRS interview.
- To prevent bias on SCoRS rating, raters of SCoRS should remain blinded to the patient's performance on both MCCB and VRFCAT and MUST be different from the person administering MCCB and VRFCAT.

Proprietary confidential information © 2024 Boehringer Ingelheim International GmbH or one or more of its affiliated companies

- During the MCCB assessments and throughout the visit, patients are allowed to take short breaks as needed, in the judgement of the rater/investigator.
- In case of patient experiences acute episode of schizophrenia (relapse), all efficacy assessments MUST be rescheduled (even if outside the visit window) until patient stabilizes, per investigators judgment. All safety assessments including PANSS, C-SSRS should be conducted, if possible.

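### Section 5.2.5 offers the CGI-S as an aid for judging schizophrenia worsening or relapse, but this trial's CGI-S rates cognitive impairment, the drug's target, not psychotic symptoms

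*Protocol*

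**What the plan says.** Protocol Section 5.2.5 (Other safety parameters) covers assessment of the disease state. It begins with the PANSS ("PANSS will be used to evaluate the disease severity") and adds: "In addition investigator may use CGI-S and his/her clinical judgment for assessing schizophrenia worsening/relapse".

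It then describes two adverse events:
- *Worsening* (deterioration of residual symptoms) is managed and reported by the investigator's clinical judgement. No other criterion is given.
- *Relapse* (acute episode) is "Increased level of care (such as hospitalization, home hospitalization, emergency room (ER) visit due to psychotic symptoms") that is "due to worsening of psychotic symptoms / increased PANSS per investigators judgment". No CGI-S threshold appears.

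Section 5.1 says the CGI-S "is a one-item evaluation completed by the clinician on the patient's severity of cognitive impairment", rated from 1 (none) to 4 (severe). Section 6.2.1 tells the rater how to arrive at it: "The CGI rater should base their assessment after review of information about that patient at that visit for CGI-S". The same sentence names the SCoRS interview as part of that information. No other CGI-S is defined in the protocol or SAP.

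Protocol Section 2.2.2.2 lists "Incidence of relapse" as a further safety endpoint. SAP Table 6.3: 1 uses schizophrenia adverse events to classify some treatment interruptions and stops for the primary estimand.

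**The concern.** A reader used to the conventional CGI-S would take the Section 5.2.5 sentence to mean a global rating of schizophrenia severity. Under Section 5.1 it means something else. An investigator who follows the text judges a psychotic safety event with help from an efficacy rating of the construct the drug targets.

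Errors can go both ways. Improved cognition can make a psychotic deterioration look milder than it is, and a cognitive decline with stable psychosis can be recorded as worsening. If the drug has no effect on cognition, this adds noise equally to both arms. If the drug improves cognition, both errors tend to lower the recorded count on active relative to placebo, so the safety comparison would look somewhat better than it should.

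Worsening is the more exposed event because it has no anchor beyond judgement. Relapse is less exposed: the CGI-S could enter only where the investigator attributes an increased level of care to psychotic symptoms. Section 1.4.2 says a relapse definition is provided so that relapse is monitored in a standardised way; an optional tool that rates something else works against that aim.

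**Working it through.** The plan states no figure on this point, so the check is mainly a reading of the sections against each other, followed by a bound on how far the problem could reach.

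**Step 1. Does the scale fit its use?** Section 5.2.5 needs a measure of psychotic symptoms. Section 5.1 supplies a measure of cognitive impairment, and Section 6.2.1 ties it in part to an interview about cognition. The two do not fit.

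**Step 2. When is the CGI-S available?** The SAP Section 6.7 analysis windows put post-baseline CGI-S at Weeks 12, 24 and 26, and PANSS at Weeks 12 and 26. At Week 24 the CGI-S is planned and the PANSS is not. Against that, Section 6.2.1 defers all efficacy assessments during an acute episode while the PANSS is still done, and the CGI-S is described under efficacy. So one section offers for judging relapse a scale that another would postpone once relapse is recognised.

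**Step 3. Illustration for the adverse events.** The documents give no rate of worsening and no frequency of reliance on the CGI-S. Assume 5% to 10% of patients worsen and the CGI-S changes the call in 5% to 10% of those:
- patients who worsen per arm: 293 × 0.05 = 15 to 293 × 0.10 = 29
- calls changed per arm: 293 × 0.05 × 0.05 = 0.7 to 293 × 0.10 × 0.10 = 2.9

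**Step 4. Can it reach the primary analysis?** Under SAP Table 6.3: 1, off-treatment data are kept when the event behind an interruption or stop has the category 'Schizophrenia Relapse' or the preferred term 'Schizophrenia'. Calling a relapse a worsening therefore changes nothing if the event still codes to 'Schizophrenia'. Data handling changes only if all of these hold:
- treatment is interrupted or stopped;
- an outcome is collected after the 12-day residual effect period (and, for an interruption, before restart);
- the event has neither identifier;
- no other treatment-policy event applies (for permanent stops, for example, a drug-related adverse event).

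**Step 5. Outer bound for permanent stops.** Inputs from Protocol Section 7.5: 30% to 40% stop early; 25% to 50% of these have later outcomes; 293 per arm; standardised effect 0.35; SD about 5.8. As a check on these inputs, 220 per arm at 0.35 and one-sided 0.025 gives 95.6% power, matching Table 7.5: 1.
- share with outcomes after stopping: 0.30 × 0.25 = 7.5% to 0.40 × 0.50 = 20%, or 22 to 59 per arm
- assumption: 5% to 25% of these stopped for psychotic worsening, or about 1 to 15 per arm
- worst case: all of these on active move from kept to excluded, and their data carried none of the effect. Shift = share × 0.35
- low end: 0.075 × 0.05 × 0.35 = 0.0013 SD (× 5.8 = 0.01 T-score points)
- high end: 0.20 × 0.25 × 0.35 = 0.0175 SD (× 5.8 = 0.10 points)
- at the high end the apparent effect is 0.3675 and power moves from 95.6% to 97.1%

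**The case against.** The strongest reply is that this is loose wording with little practical effect. The CGI-S is permitted, not required, and it supplements the PANSS. Relapse has its own definition, built on level of care and psychotic symptoms or PANSS. Efficacy scales are deferred during an acute episode. Independent cross-checks exist: PANSS total score and change are reported as safety outputs, and health-care resource use records hospitalisations, home hospitalisations and emergency visits due to psychotic symptoms. Section 6.2.1 also bases the CGI-S on patient information that includes the SCoRS interview, not on that interview alone. Finally, even a small deletion is a protocol amendment needing ethics and authority review in about 14 countries.

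Most of this stands, and it limits the consequences. It does not remove the mismatch. The deferral applies once relapse is recognised, whereas Section 5.2.5 concerns the judgement that leads there. The level-of-care anchor does not protect the worsening event.

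A reader might go further and infer that a drug effect on cognition would lower recorded relapse and so change which data the primary analysis keeps. The documents do not support that. The preferred-term route keeps data whichever label is used, provided the event codes to 'Schizophrenia', and the remaining conditions must all occur together. Protocol Section 7.2.2 also plans supplementary analyses that treat all intercurrent events by treatment policy, or all as hypothetical; neither depends on this classification.

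**Conclusion.** The point holds as an inconsistency between Protocol Sections 5.1 and 5.2.5 that bears on safety adverse events. The main exposure is worsening; the relapse endpoint is exposed to a lesser degree, through attribution. The number of calls affected cannot be derived from the documents. The figure of roughly 1 to 3 per arm rests wholly on assumed rates.

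The effect on the primary analysis is indirect and probably negligible. The ceiling of about 0.018 SD assumes that a quarter of post-stop outcomes follow psychotic worsening and that every such active-arm patient is reclassified, which an optional aid would not bring about. It covers permanent stops only; the documents give no rate of temporary interruptions from which to size those. If the drug has no cognitive effect, the CGI-S does not differ by arm through this route, so it creates no false positive on the primary endpoint.

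**What to change.** Reconcile Sections 5.1 and 5.2.5. Remove the CGI-S from the Section 5.2.5 sentence, leaving the PANSS, level of care and clinical judgement that the section already names. Add one line saying that the CGI-S in this trial is a cognition rating and is not used to assess worsening or relapse. The line matters because deletion alone would not stop an investigator who knows the rating from weighing it.

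The cost is one edited sentence, one added line and a site reminder. No data are lost, and the CGI-S assessments and the SAP analyses stay as they are. The change does not justify an amendment of its own; it can go into the next one.
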